3.2.5 Extended Maintenance Period (All Treatment Pathways)

The last treatment period for all treatment pathways is the Extended Maintenance Period. Subjects who completed initial maintenance in the parent AR101 study (Treatment Pathways 1 and 4) will enter the Extended Maintenance Period after the Screening/Baseline visit, and the other subjects (Treatment Pathways 2, 3, and 5) will enter the Extended Maintenance Period after completing the Initial Maintenance Period in this study, after completing both the Repeat Up-Dosing and Initial Maintenance Periods in their parent study, or after receiving AR101 300 mg OD for at least 24 weeks in their parent study.

During the Extended Maintenance Period, subjects will continue their current dosing regimen (300 mg QD, BIW, QW, or QOW) so long as they continue to tolerate it. At any point during ARC008, subjects on nondaily dosing regimens may switch to Treatment Pathway 2 and enter Repeat Up-Dosing if they do not tolerate nondaily dosing.

For subjects continuing nondaily dosing, the dosing intervals should be as consistent as possible, preferably on the same day(s) each week.

- For BIW dosing regimen, doses should be at least 3 days apart (eg, Monday and Thursday each week)
- For QW dosing regimen, doses should be taken on the same day (±1 day) each week

- ARC008 Protocol Amend 6.0
- For QOW dosing regimen, doses should be taken on the same day (±2 days), every alternate week
- Study visits will occur approximately every 3 months until the study ends (Section 3.6).

Subjects in Treatment Pathways 1, 2, and 3 who enter this period will have the option to participate in an OLFC to assess level of desensitization to peanut protein after 12 months in the Extended Maintenance Period and yearly thereafter. For subjects in Treatment Pathways 4 and 5, the OLFC after the first 12 months of extended maintenance treatment is required and then optional yearly thereafter.

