3.2.6 End of Treatment Visit (All Treatment Pathways)

After protocol amendment 6.0 is approved at the study site:

- Subjects in the US from prior studies ARC007 and ARC011 who have access to commercially available product will have the End of Treatment visit at their next scheduled study site (not remote) visit.
- Subjects in the US from prior studies ARC002 or ARC004 who have access to commercially available product may have the End of Treatment visit at their next scheduled study site (not remote) visit if so directed by the study sponsor when necessary for operational considerations.
- Subjects from prior study ARC005 will return to the study site for the End of Treatment visit when they complete at least approximately 3 years total of AR101 treatment including study ARC005 and AR101 is commercially available in their country, or discontinue early.
- All other subjects will return to the study site for the End of Treatment visit when they complete at least approximately 5 years total of AR101 treatment including all prior studies and AR101 is commercially available in their country, or discontinue early.

A DBPCFC will be performed at the End of Treatment visit; subjects who discontinue AR101 treatment early for safety reasons will not have the DBPCFC. All subjects will have telephone follow-up at least 14 days after the last dose of AR101 or last food challenge, whichever is last.

Subjects with unresolved AEs at early discontinuation or at the end of AR101 treatment, or who have GI AEIs, will have safety follow-up (Section 4.4.2, Section 8.1.4.2).

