9.1 Sample Size

There is no sample size calculation for this study. The sample size will be determined by the number of eligible subjects from each of the prior AR101 studies who participate in this study.

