6. GENERAL ASPECTS FOR STATISTICAL ANALYSIS

6.1. STATISTICAL NOTATION AND METHODOLOGY

Unless otherwise stated, the term "descriptive statistics" refers to the number of subjects (n), mean, median, standard deviation, minimum, and maximum for continuous variables and frequencies and percentages for categorical variables.

Unless specified otherwise, the denominator for percentages for categorical data will be based on the number of subjects or observations with non-missing data appropriate for summary purposes. The denominator for percentages for incidence data (such as AEs) will be based on the number of subjects in the analysis population "at risk". Select ordinal data may be summarized using both descriptive statistics and counts and percentages of subjects in each category, as appropriate.

Minimum and maximum values will be presented at the precision of the original value, means and medians will be rounded to 1 decimal place greater than the precision of the original value, standard deviations and standard errors will be rounded to 2 decimal places greater than the precision of the original value. Percentages will be rounded to 1 decimal place. Percentages that round down to 0 or up to 100% will be displayed as "<0.1%" and ">99.9%", respectively. Other statistics (e.g., confidence intervals [CIs]) will be presented using the same general rules outlined above or assessed for the most appropriate presentation based on the underlying data.

Unless otherwise noted, values reported as greater than or less than some quantifiable limit (e.g., "< 1.0") will be summarized with the sign suppressed in summary tables and figures, using the numeric value reported. Data will display on subject listings to include the sign.

In general, summary tables will be presented by combining subjects from each of the treatment pathways into a single treatment group (AR101).

All relevant data collected in the database and any derived data will be included in data listings and unless otherwise noted sorted by treatment pathway, subject ID, test/measurement, and visit and time point as appropriate.

All statistical methods will be based on the International Conference on Harmonisation (ICH)-E9 Guidance for Industry "Statistical Principles for Clinical Trials".

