6.3. SUBGROUP ANALYSES

The overall summary of treatment-emergent adverse events (TEAEs) and treatmentemergent serious adverse events (TESAEs) (Section 9.1) and the summary of rescue medications (Section 9.12) will be repeated for the following subgroups:

- Treatment Pathways 1-3
- Treatment Pathways 4-5
- Daily dosing regimen
- Non-daily dosing regimen

Daily and non-daily dosing regimen subgroups are based on the initial regimen assigned in ARC008.

The overall summary of treatment-emergent AEs of interest (AEIs) and treatmentemergent serious AEIs will also be summarized separately for Treatment Pathways 1-3 and 4-5.

Immunoglobulin values will also be summarized separately for Treatment Pathways 1-3, 4, and 5.

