For each OLFC and DBPCFC at End of Treatment, the proportion of subjects who tolerate each challenge dose (3 mg, 10 mg, 30 mg, 100 mg, 300 mg, 600 mg, 1000 mg, and 2000 mg) of peanut protein with no more than mild allergy symptoms will be assessed using the Safety Population. Desensitization response rates and associated 95% CIs will be presented using exact Clopper Pearson CIs. The number and percentage of subjects at each dose level for MTD will also be summarized. Summaries for the OLFCs will be presented at each time point (End of Initial Maintenance, Extended Maintenance every year) and by years of total AR101 exposure (including parent studies) and overall. A summary of the DBPCFC at End of Treatment will be presented for each treatment pathway by years of total AR101 exposure and overall.

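### OLFC response and maximum tolerated dose are tabulated over time with no pathway split, so the rows appear pooled while the mix of subjects tested changes by design

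*SAP*

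**What the plan says.** For the open-label food challenge (OLFC), SAP 10.1 promises response rates with exact Clopper-Pearson intervals and the distribution of maximum tolerated dose (MTD): "Summaries for the OLFCs will be presented at each time point (End of Initial Maintenance, Extended Maintenance every year"), then by years of total AR101 exposure and overall. Pathway is not mentioned. The next sentence treats the blinded challenge differently: "A summary of the DBPCFC at End of Treatment will be presented for each treatment pathway by years of total AR101 exposure and overall".

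The default is in SAP 6.1: "In general, summary tables will be presented by combining subjects from each of the treatment pathways into a single treatment group (AR101"). SAP 6.3 lists the exceptions. For immunology it says "Immunoglobulin values will also be summarized separately for Treatment Pathways 1-3, 4, and 5". It lists no OLFC subgroup, and SAP 6.2 plans no stratification or adjustment. OLFC results by pathway appear only in subject listings.

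Coverage differs by pathway:

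- SAP 7.1.1, Table 1, defines an End of Initial Maintenance window for Pathway 5 only.
- Protocol 3.2.5 makes later challenges optional for everyone and makes the Month 12 challenge optional in Pathways 1 to 3. For the ARC005 pathways, "For subjects in Treatment Pathways 4 and 5, the OLFC after the first 12 months of extended maintenance treatment is required".
- Protocol 3.2.6 sets a shorter planned treatment for the same children: "Subjects from prior study ARC005 will return to the study site for the End of Treatment visit when they complete at least approximately 3 years" of AR101 in total. The remaining subjects have a 5-year target, apart from US subjects from some parent studies, who may or must leave sooner. Both targets also require AR101 to be commercially available in the subject's country.

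**The concern.** Protocol 1.3 asks whether desensitization is maintained or keeps increasing with longer treatment. That is a question about change over time. SAP 13 withdraws the within-subject endpoint, change in tolerated dose, from both listing and summary. The successive OLFC rows are then the main summarised evidence on change during treatment.

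If those rows pool all pathways, they compare different people. ARC005 enrolled children aged 1 to under 4 years; the other parent studies enrolled from age 4 upward. At Month 12 the ARC005 children are tested by requirement and the others by choice. From about Month 36 the rows are expected to be mainly volunteers from Pathways 1 to 3. A rise or fall down the table could come from that shift alone, and a reader would have no tabulated way to tell.

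**Working it through.** The protocol says "There is no sample size calculation for this study", so there is no planned figure to reproduce. The check is of the timeline and of simple mixing arithmetic.

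**1. When ARC005 subjects reach planned end of treatment.** Pathway 4 enters Extended Maintenance after about 12 months of AR101 in ARC005 (Protocol 1.2.5). Pathway 5 enters after about 12 months in ARC008 (Protocol 3.2.4). Three years in total is therefore 36 − 12 = Month 24 of Extended Maintenance.

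**2. When Pathway 3 subjects reach theirs.** Up-dosing lasts 22 to 52 weeks and initial maintenance 24 weeks, so 46 to 76 weeks precede Extended Maintenance. Five years in total is 60 − (46 × 7 / 30.4375) = Month 49.4 at the latest and 60 − (76 × 7 / 30.4375) = Month 42.5 at the earliest.

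**3. Whether exposure bands separate the groups.** At Extended Maintenance Month 12, Pathways 4 and 5 have about 1 + 1 = 2.0 years of AR101. Pathway 3 has (46 × 7 + 365.25) / 365.25 = 1.9 years to (76 × 7 + 365.25) / 365.25 = 2.5 years. They fall in the same one-year bands, so the split by exposure does not remove the mixing.

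**4. Size, as an illustration.** Inputs from the documents: about 132 subjects in ARC005 (Protocol 1.2.5) and about 950 potential subjects in ARC008 (Protocol 3.5), leaving 950 − 132 = 818 others. Assumptions not in the documents: all 132 are tested at Month 12; a fraction u of the 818 choose the challenge; no ARC005 subjects are tested at Month 36; the groups differ in response by d points at a given dose; each group's own rate stays constant; and percentages are of subjects challenged, following the non-missing-data rule in SAP 6.1.

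ARC005 share at Month 12 = 132 / (132 + 818u). Shift in the pooled rate from Month 12 to Month 36 = share × d.

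| u | Others tested | ARC005 share | Shift, d = 10 | Shift, d = 30 |
|---|---|---|---|---|
| 30% | 245.4 | 35.0% | 3.5 | 10.5 |
| 50% | 409.0 | 24.4% | 2.4 | 7.3 |
| 80% | 654.4 | 16.8% | 1.7 | 5.0 |

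**5. Sensitivity at u = 50%.** If only 66 ARC005 subjects are tested at Month 12, the share is 66 / (66 + 409) = 13.9% and the shift is 1.4 to 4.2 points. If all 132 are tested at Month 12 and 33 of them again at Month 36, the later share is 33 / (33 + 409) = 7.5%. The fall in share is then 16.9 points, and the shift at d = 30 is 5.1.

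**6. Effect of the split.** With separate columns for Pathways 1-3, 4 and 5, the part of the shift caused by a changing ARC005 share is zero by construction.

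**The case against.** The strongest reply is that the study is descriptive, with no comparison over time planned, so no planned estimate is biased. That is correct: the risk is a misread table, not an error rate. It is also fair that Protocol 3.4.2 assigns desensitization after longer-term treatment to the End of Treatment blinded challenge, which SAP 10.1 does summarise by pathway. The secondary objective does not rest on the OLFC rows alone. That challenge is nevertheless a single point per subject at the end of treatment, so it does not show the course during treatment.

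Pooling is an inference. The SAP 6.1 rule is only a general one, and the table shells are a separate document. The contrast with the blinded challenge and the immunoglobulins makes pooling likely, not certain.

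A reader might also go further than the documents allow:

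- *That ARC005 children leave soon after Month 12.* The earliest planned exit under the 3-year rule is about Month 24, so they can still contribute to that row, whose window is 18 to under 30 months.
- *That they are absent by Month 36, or that the bands of 3 years and over are almost entirely Pathways 1 to 3.* The 3-year target is a minimum and depends on commercial availability. Subjects without access continue, and Protocol 6.2.2 also allows an optional OLFC at End of Treatment. No count of leavers is given.
- *That the required challenge is free of selection.* Only children still on treatment at Month 12 are tested.

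The figures are hypothetical too. 132 assumes that every ARC005 subject rolls over and is tested, and neither uptake nor the response difference has a source in the documents.

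**Conclusion.** The point holds as a reporting weakness. SAP 10.1 leaves the OLFC summaries without a pathway split, so they appear to be pooled. The subjects behind successive rows change by design, and the exposure bands do not correct for it. On the stated assumptions, the pooled rate shifts by about 1.7 to 10.5 points between Month 12 and Month 36 with no change in either group.

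The direction is unknown: the apparent trend falls if ARC005 children respond better than the others and rises if they respond worse. The shift is smaller if fewer ARC005 subjects are tested or some remain at Month 36. It is larger if fewer of the 818 others are present or volunteer. The range is an illustration, not a bound or a forecast. What the documents do support is that a pooled row at Month 12 and one at Month 36 or later should not be read as a trend.

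**What to change.** In SAP 10.1, present OLFC response and MTD separately for Treatment Pathways 1-3, 4 and 5 at each time point and exposure band, using the grouping already in SAP 6.3. Beside each row give the number tested out of the number still on treatment. Footnote any pooled row as not comparable over time. A same-subject summary for those with repeat OLFCs would help, because it holds the subjects fixed.

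Add a note that the Pathway 1-3 column is still not a clean trend. Testing there is optional throughout, and US subjects from ARC007 and ARC011 with access to commercial product end treatment at their next site visit after Amendment 6.0.

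The programming cost is small, since the data are already listed by pathway. The price is smaller cells and wider Clopper-Pearson intervals. SAP 1.1 says that Version 2 was written after database lock and is confined to Appendix A, so the added tables should be labelled post hoc and exploratory, as SAP 6.1 requires.

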10.2. MAXIMUM SEVERITY OF SYMPTOMS IN EACH FOOD CHALLENGE

The maximum severity of allergy symptoms after consuming peanut protein during each food challenge (OLFC or DBPCFC) will be included in the subject listings.

Symptom severity is determined according to the CoFAR scale at 5 levels: 1-Mild, 2-Moderate, 3-Severe, 4-Life-threatening, and 5-Fatal. Analysis is done on 4 levels: 0-None, 1-Mild, 2-Moderate, 3-Severe or higher (severe, life-threatening, fatal). Subjects who experience no symptoms will be assigned a severity of 0-None. Symptom severity data are collected at each challenge dose of peanut protein during the OLFC and DBPCFC (for dose levels 3 mg, 10 mg, 30 mg, 100 mg, 300 mg, 600 mg, 1000 mg, and 2000 mg); the maximum severity of symptoms observed at any of these dose levels will be listed for each subject.

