9.6 Efficacy Analyses

All efficacy endpoints will be summarized using descriptive statistics. Further details will be provided in the SAP.

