3.2. EFFICACY ENDPOINTS

The secondary efficacy endpoints are as follows:

• Proportion of subjects tolerating each challenge dose in the OLFC and the DBPCFC

- The maximum tolerated challenge dose at each food challenge
- Change in tolerated dose of peanut protein
- Maximum severity of symptoms in each food challenge
- Frequency of use of epinephrine as a rescue medication during the food challenges
- Changes in food allergy QoL scores as measured by Food Allergy Quality of Life Questionnaires (FAQLQ), and the Food Allergy Independent Measure (FAIM) questionnaire
- Change in Food Allergy Quality of Life Parental Burden (FAQL-PB) questionnaire score

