6.5. SIGNIFICANCE LEVEL

No formal statistical analysis will be performed. This study is exploratory in nature; descriptive statistics will be tabulated and reviewed to evaluate all study endpoints.

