If the imputed stop date is greater than the last study date for the subject, then the imputed date will be replaced with the last known subject date.

The reported date of the most recent reaction to peanut on the peanut allergy history CRF page and date of diagnosis of peanut allergy will be imputed when the month or day is missing as follows:

- Missing day is set to 1 if the same year and month as the informed consent date. Otherwise it is set to 15.
- Missing month and day are set to Jan 1 if the same year as the informed consent date. Otherwise it is set to July 1.

Where the severity score of a symptom is missing during a food challenge (OLFC or DBPCFC), the severity score will be imputed as severe.

Where the severity score of an AE is missing, the severity score will be imputed as severe.

Where the relatedness of an AE is missing, the relatedness will be imputed as related to study product.

No imputations will be made for other missing data, unless specified otherwise.

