10. ANALYSIS OF EFFICACY ENDPOINTS

Unless otherwise noted, efficacy data will be summarized descriptively, and the Safety Population will be used for all summaries of efficacy parameters. Efficacy listings will include all enrolled subjects, sorted by treatment pathway.

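### Maximum symptom severity at food challenges, a secondary efficacy endpoint, is only listed in the SAP text, and Section 13 does not declare this

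*SAP*

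**What the plan says.** SAP 3.2 names "Maximum severity of symptoms in each food challenge" as a secondary efficacy endpoint, and Protocol Table 1 places it under the secondary objective on desensitization.

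Three general statements cover its analysis:
- Protocol 9.6: "All efficacy endpoints will be summarized using descriptive statistics".
- SAP 6.5: "descriptive statistics will be tabulated and reviewed to evaluate all study endpoints".
- SAP 10, opening paragraph: "Unless otherwise noted, efficacy data will be summarized descriptively".

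SAP 10.2 is the endpoint's own section. It takes the five CoFAR grades, adds a level for no symptoms, and merges the top three grades: "Analysis is done on 4 levels: 0-None, 1-Mild, 2-Moderate, 3-Severe or higher". On output, it says that the maximum severity "will be included in the subject listings", and closes by repeating that "the maximum severity of symptoms observed at any of these dose levels will be listed for each subject". It gives no table, time points, denominator or grouping.

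SAP 7.5 adds that where a challenge symptom has no severity, "the severity score will be imputed as severe".

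SAP 13 declares seven items for which raw values are listed but change values are neither listed nor summarized: three secondary safety, three secondary efficacy and one exploratory. It also notes that real world peanut challenge results go to listings. Maximum symptom severity is not mentioned.

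**The concern.** An analysis scale that feeds only a listing produces no result. If 10.2 is followed as written, a planned secondary endpoint reaches the study report with no count or percentage, and the section meant to record departures from the protocol is silent about it.

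The endpoint adds something that the response rates lack. A challenge dose is either tolerated or not; severity shows what the failures looked like. Protocol 1.4.2 relies on this measure. It cites maximum severity at the DBPCFCs as a key secondary result of the parent studies, and uses the reduced severity to argue that reactions to unintended exposure should be milder on treatment. A longer-term study that lists the same measure without tabulating it cannot readily show whether that finding persists.

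**Working it through.** No power, error rate or event figure is involved, so the check sets the texts side by side.

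**Step 1. What happens to each secondary efficacy endpoint in SAP 3.2?**

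| Endpoint | Treatment in the SAP text |
|---|---|
| Proportion tolerating each challenge dose | Tabulated with exact 95% CIs (10.1) |
| Maximum tolerated dose | Tabulated, n and % per dose level (10.1) |
| Epinephrine use during challenges | Within the rescue medication summary, separately for OLFCs and DBPCFCs (9.12) |
| Change in tolerated dose | Change declared as dropped (13) |
| Changes in FAQLQ and FAIM | Change declared as dropped (13) |
| Change in FAQL-PB | Change declared as dropped (13) |
| Maximum severity of symptoms | Listed only (10.2); not declared in 13 |

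The count is 3 tabulated + 3 declared + 1 neither = 7.

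**Step 2. Does another table carry the information?**
- TEAE summaries exclude symptoms recorded during food challenges (SAP 9.1).
- Allergic reactions during challenges are not reported as AEIs. The AEI summary keeps anaphylactic reactions at challenges only if they were serious (SAP 9.2).
- Treatment-emergent anaphylaxis excludes reactions during or related to a challenge (SAP 9.2.1).
- The response and MTD tables treat a dose as tolerated only if symptoms were at most mild and not dose-limiting (SAP 7.3, 10.1). A moderate and a severe reaction at the same dose give the same entry.

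A severe but non-serious challenge reaction therefore enters no severity table.

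**Step 3. Is the missing-severity rule evidence that a table was intended?** Not by itself. Setting a missing severity to severe also settles whether a dose met the at-most-mild condition in 10.1, so the rule has a use without a severity table. It does bear on presentation: imputed values fall in the top level of the four-level scale, so their number should be visible.

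**Step 4. What can be said about volume?** About 950 is the potential enrolment (Protocol 3.5). OLFCs are optional throughout for Pathways 1 to 3, and optional after the first extended-maintenance OLFC for Pathways 4 and 5 (Protocol 3.2.5). The Study Exit DBPCFC is optional (3.2.8). Subjects who stop early for safety reasons have no End of Treatment DBPCFC (3.2.6). The study also ended well ahead of expectation (SAP 7.7). No number of challenges can be derived.

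**The case against.** The best defence is that a table may well be planned. SAP 10 makes a descriptive summary the default, SAP 6.5 promises tabulation for all endpoints, a stated analysis scale fits both, and the output index sits in a shell document outside the protocol and SAP (SAP 18). This stands as a reason for caution, but it does not rescue 10.2. The default yields where something else is noted, and 10.2 notes listings twice. If the default nevertheless governs, 10.2 is incomplete: unlike 10.1, it gives no time points, denominator or exposure grouping. Either reading needs a correction.

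A second defence is that reactions at challenges are partly covered by the response rates, rescue medication use and serious anaphylaxis. This is fair. The desensitization objective is not left without information on reactions; what is missing is the grading of the failures.

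Third, the listing is openly stated in 10.2, and Version 1 of the SAP was approved before database lock. A reader might infer concealment, which the documents do not support. The lapse is a missing entry in Section 13.

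Fourth, SAP 6.1 expects changes to the planned analysis before lock, and Version 2 is post-lock with edits confined to Appendix A. A table specified now has a layout chosen after lock and must say so. That does not make the endpoint post hoc: the endpoint and its four levels were prespecified.

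**Conclusion.** The conflict is real and limited to descriptive reporting. SAP 10.2 does not deliver what Protocol 9.6 and SAP 6.5 promise, and this is the one secondary efficacy endpoint of seven that is neither tabulated in the SAP text nor declared in Section 13. No hypothesis test, error rate or primary endpoint is touched. The conclusion assumes that 10.2 means what it says about output; the table shells could show otherwise.

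Three stronger readings are tempting and should be resisted:
- A reader might infer that this is the only secondary efficacy endpoint without a summary. Three others lose their change summaries too; the difference is that Section 13 says so.
- A reader might infer that a maximum-severity table would reveal how often severe reactions occur at 2000 mg. The endpoint is the worst severity at any dose, so a table of it has no dose dimension.
- A reader might infer a listing of some 950 subjects with several challenges each. Potential enrolment and mostly optional challenges do not support that figure.

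**What to change.** Add one table to SAP 10.2: n (%) at levels 0 to 3, with subjects challenged as the denominator, for each OLFC time point, the End of Treatment DBPCFC and the optional Study Exit DBPCFC. Present it by years of total AR101 exposure and overall, and show how many severities were imputed as severe. If severity at 2000 mg is of interest, add rows by challenge dose; severity is already collected per dose.

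Because the database is locked, the study report should state that the endpoint was prespecified and that the table layout was set after lock.

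If no table is produced, Section 13 and the study report must declare the endpoint as listed only.

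The cost is small. The maximum is already derived for the listing, so the first option is one table and a sentence in the report, and the second is one line in each document. By-dose rows would need some further programming. Since Version 2 confines its edits to Appendix A, a change to 10.2 or 13 means a further SAP version.
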